Screening Run-In (3 days): The participant will receive daily email links to an online sleep diary and three questionnaires: the IRLS subscale, SOWS, and an opioid craving visual analog scale. Baseline subjective sleep measures will be determined from this 3-day period.

RANDOMIZATION VISIT (VISIT 3) AND TREATMENT PERIOD:

A more thorough medical history will be collected at the Randomization Visit, along with demographic information. At this visit, the 3-day sleep diary and questionnaire results will be reviewed for final eligibility before the participant is randomized to treatment.

Eligible participants will be randomized in a 1:1 ratio to 10 days of placebo or pramipexole. Pramipexole will be started at 0.25 mg nightly for the first 3 days. On day 3, a study physician will call the participant over the phone or on video to inquire about efficacy and adverse events (Visit 4). Visit 4 may occur on day 4 or 5 if the study physician is unable to meet on day 3. If the 0.25-mg dose is well tolerated but not effective, the dose can be increased to 0.5 mg.

Participants will receive medication from the Gavin Foundation staff and will complete the online sleep diary and questionnaires every day (see the Table of Procedures below for the exact schedule). Gavin Foundation staff will direct participants to the secure computer on which they can complete the sleep diary and questionnaires.

FINAL STUDY VISIT (VISIT 5):

On Day 10, participants will meet with a study physician. The physician will assess the participant on the Clinical Global Impression-Improvement (CGI-I) scale and will also inquire about any adverse events experienced. If a participant is discharged from the Gavin Foundation CSS before Day 10, study staff will attempt to perform Visit 5 before his or her departure from the facility.

Compensation:

Participants will be remunerated. Any earnings will be loaded onto a debit card, which will be given to the participant when he or she leaves the Gavin Foundation CSS.

Participants will be paid based on completion of sleep diaries and questionnaires after receiving study drug.

The payment schedule is as follows:

- \$5/day for filling out diaries and questionnaires on the 10 days on study drug
- \$25 for fully completing the study (i.e. spending 10 days on the study drug and completing 10 days of diary entries)

The total possible compensation is \$75.

[figure not shown]

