This research has potential benefits to society: this study may help other people with OUD and RLS symptoms by adding to the knowledge about this drug, and whether it is a beneficial treatment.

IX. BIOSTATISTICAL ANALYSIS

Analysis of all study data will be conducted by [name], [name], and [name] or another statistician at Partners Healthcare hospitals. All study personnel and participants will remain blinded to treatment assignment, including staff entering study data. Only the hospital Research Pharmacist who generates the randomization code and [name] who will conduct the interim analysis will be unblinded to treatment assignment. The final database will not be unblinded to study staff until all study data are complete and a medical and scientific review by [name] is conducted.

Overview of analytic plan:

We will conduct an interim analysis to probe the futility of the study. We will use the data obtained to date to estimate the effect of randomized treatment group on two outcomes (primary outcome: IRLS score; secondary outcome: SOWS). We will then use this estimate to determine the sample size necessary to detect this effect. To protect the blind, a statistician ([name]) who is not involved in the day-to-day running of the study, will conduct the analyses.

We will perform both intent-to-treat (ITT) analyses (including all patients who received one dose of study medication and complete one assessment post-randomization) and per protocol analyses (including participants with 10 days of evaluable data). Distributions of the outcomes will be examined and data transformation will be applied to satisfy the normality assumptions.

We will analyze data in several ways: comparison of change from randomization to end of Day 5; comparison of change from randomization to end of Day 10; and using all daily values (i.e., longitudinal analyses). The two groups are drug and placebo.

Study endpoints:

The primary outcome (IRLS score) and all secondary and exploratory measures are continuous variables. We will modify the IRLS in two ways: (i) only the symptoms subscale will be employed (only items 1, 2, 4, 6, and 8 will be included); and (ii) the questions will be modified to include symptoms for only the last 24 hours rather than for the previous 7 days. Primary

analyses will focus on the difference in the change in IRLS subscale from randomization to Day 5 and from randomization to Day 10 between the two groups.

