The key secondary variables are the difference from randomization to Day 5 and from randomization to Day 10 in SOWS.

Exploratory analyses will similarly focus on the differences from randomization to Day 5 and from randomization to Day 10. These endpoints include:

- 1. Subjective total sleep time
- 2. Subjective sleep latency
- 3. Subjective time awake after sleep onset
- 4. Depressive (PHQ-9) and anxiety (GAD-7) symptoms
- 5. Time spent in the Gavin CSS

STATISTICAL METHODS

Interim analysis:

(i) Two-sample t-tests will be applied to estimate the effect of randomized treatment group on IRLS subscale score, for the subjects with post-randomization data to date. Using the estimated treatment effect, we will conduct a power analysis to determine the sample size necessary to detect this effect. (i) Two-sample t-tests will be applied to estimate the effect of randomized treatment group on SOWS, for the subjects with post-randomization data to date. Using the estimated treatment effect, we will conduct a power analysis to determine the sample size necessary to detect this effect.

Primary analysis:

(i) Two-sample t-tests will be applied to compare the change in IRLS subscale from randomization to Day 5 and from randomization to Day 10 between the two groups. (ii) Linear mixed-effects models will also be applied to the longitudinally measured IRLS subscale with entry of covariates that correlate with changes in primary endpoints as required (e.g., age, sex, and at-randomization levels of IRLS severity, and SOWS). Subjective sleep measures from the sleep diary for every night of data collection will also be added as potential covariates to the linear mixed-effects models.

Secondary Analysis:

(i) Two-sample t-tests will be applied to compare the change in SOWS from baseline to Day 5 and to Day 10 between the two groups. (ii) Linear mixed-effects models will also be applied to longitudinally measured SOWS with entry of covariates that correlate with changes in primary endpoints as required (e.g., age, sex, and at-randomization levels of IRLS severity, and SOWS).

Subjective sleep measures on every night of data collection will also be added as potential covariates to the linear mixed-effects models.

Exploratory Analyses:

Linear and generalized linear mixed-effects models will be applied to compare changes in the self-reported sleep metrics (e.g., quality, disturbance, sleep latency and duration) across the nights of study and between the groups.

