Linear and generalized linear mixed-effects models and survival-based analyses will be applied to compare the number of days patients continue in CSS treatment between the two groups.

Power/Sample Size:

Power calculations are based on Specific Aims 1 and 2 detailed below. There are insufficient published or unpublished data to perform them on exploratory analyses (detailed above). Meta-analyses of RLS clinical trials indicate that placebo effects using the IRLS are strongly related to the duration of these trials (Fulda et al., 2008). Therefore, we are basing our calculations on short-term trials, similar to our study design, for pramipexole in RLS using abbreviated RLS symptom scales (e.g., Oertel et al., 2007; Manconi et al., 2007, 2012)

Aim 1: The primary outcome is the change in IRLS scale from baseline to Day 10. Using the Oertel et al. (2007) data as reference, with n=34 for each group, we will have 80% power to detect a 6.3 points difference in the change of IRLS scale (with a common standard deviation of the change of 9.0) with a two-sided two-sample t-test at alpha=0.05 level. A change of 3 is considered a clinically meaningful difference from placebo (Allen et al., 2013).

Aim 2: The primary outcome is the change in SOWS. Using the Dunn et al. (2017) data as reference, with n=34, we will have 80% power to detect a 4 points difference in the change of SOWS (with a common standard deviation of the change of 6.0) with a two-sided two-sample t-test at alpha=0.05 level.

Therefore, our plan is to enroll 160 people in a 1:1 drug:placebo ratio in order to randomize 88 patients with OUD and have 68 participants complete the 10-day trial. With approximately 16 patients per week admitted to the CSS with opioid use disorder, and an RLS prevalence of 50% in this context, we do not anticipate any difficulty enrolling to our target sample size for the trial within a 20-month enrollment period.

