Note: The study has had difficulty enrolling study participants. We originally projected that we would be able to enroll all participants within 24 months. Over the two years since we initiated enrollment, we have enrolled 70 of 160 projected participants, which is 43.7% of our enrollment target. During this period, we have randomized 35 of 68 projected participants, which is 51.5% of our randomization target. Due to this delay, we have added an interim analysis to our study protocol to assess the futility of the study. If the needed sample size is smaller than the originally projected sample size, we will continue the study. If the needed sample size is equal to or larger than the originally projected sample size, we will close the study, as we do not have the resources

to continue the study for another 24 months (i.e., the number of months it would take us to continue to recruit, given our current enrollment rate).

X. MONITORING AND QUALITY ASSURANCE

We will use a Data Safety Monitoring Board (DSMB), meeting every 6 months to review the progress of the study. The Board will comprise two research physicians who are familiar with clinical research, restless legs syndrome, OUD, opioid withdrawal, and pramipexole and its effects, but who are not collaborators or close colleagues of the PI or co-investigators. The Board will also include a biostatistician. The DSMB will review all adverse events and unanticipated problems that arise during the study. Adverse events, including serious adverse events, and unanticipated problems will be managed and reported to the IRB. The data to be monitored for safety include: withdrawal symptoms as assessed by SOWS, drug craving as assessed by craving scales, mood and anxiety scales; clinical staff at Gavin Foundation will also monitor for symptoms of hypomania/mania, impulse control disorders. [name] and/or [name], the PI and Investigator and MDs, will review these data as soon as they are available on each participant and at monthly intervals.

XI. REFERENCES

- Allen, R. P. (2013). Minimal clinically significant change for the International Restless Legs Syndrome Study Group rating scale in clinical trials is a score of 3. Sleep Medicine, 14(11), 1229-1229. doi:10.1016/j.sleep.2013.08.001
- American Psychiatric Association. (2013). Diagnostic and statistical manual of mental disorders (5th ed.). Washington, DC: Author.

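### The power section names IRLS change to Day 10 as the primary outcome, but the endpoint and methods sections list Day 5 and Day 10 as unranked primary tests

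*Combined protocol and SAP*

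**What the plan says.** The primary aim in Section II asks whether pramipexole reduces RLS symptoms significantly more than placebo. It gives no time point. Section IX then addresses the deciding comparison in several places.

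- **Overview of analytic plan.** Change to Day 5, change to Day 10 and all daily values are listed as ways to analyse the data, in no order of priority. Two analysis sets are planned, with neither called primary. That sentence reads in part: "complete one assessment post-randomization) and per protocol analyses (including participants with 10 days of evaluable data".
- **Study endpoints.** The primary "analyses will focus on the difference in the change in IRLS subscale from randomization to Day 5 and from randomization to Day 10".
- **Statistical Methods, Primary analysis.** Item (i): "Two-sample t-tests will be applied to compare the change in IRLS subscale from randomization to Day 5 and from randomization to Day 10". Item (ii): "Linear mixed-effects models will also be applied to the longitudinally measured IRLS subscale with entry of covariates that correlate with changes in primary endpoints".
- **Power/Sample Size, Aim 1.** "The primary outcome is the change in IRLS scale from baseline to Day 10". Power is given for one two-sided, two-sample t-test at 0.05, with 34 per arm, a 6.3-point difference and an SD of 9.0.

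No sentence reconciles the two-day description with the one-day description. There is no testing order, no division of alpha, and no statement on whether one significant day is enough.

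**The concern.** The power section points to one deciding test, while the two sections that define the endpoints and the analysis give equal standing to two. An analyst who follows the Primary analysis paragraph as written produces two unadjusted primary p-values. If they disagree, the plan does not say which one answers the aim. The 0.05 level in the power section describes the primary claim only if one test decides it.

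The analysis set raises a second, smaller question. Even with Day 10 fixed, the plan does not say whether the ITT or the per-protocol result is the one to be believed.

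The matter is more pressing because an unblinded interim analysis has been added. If the deciding test is chosen after interim estimates are known to those choosing, the choice can no longer be shown to be independent of the data.

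**Working it through.** **Inputs from the plan (Power/Sample Size, Aim 1):** difference 6.3, SD of change 9.0, 34 per arm, two-sided alpha 0.05. From the same section: 88 randomized for 68 completers.

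**Input not in the plan:** the correlation between the Day 5 and Day 10 test statistics. I assume 0.5 to 0.9 and show independence as the upper reference.

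**Step 1. Reproduce the plan's figure.** Standardized effect = 6.3 / 9.0 = 0.70. Noncentrality = 0.70 × √(34/2) = 2.89 on 66 degrees of freedom. Exact noncentral-t power is 81.2%. Solving for 80% power gives 33.02 per arm, which rounds up to 34. The stated sample size therefore matches a single Day 10 test at two-sided 0.05. This is a fixed-sample figure, before any effect of the interim closure rule.

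**Step 2. False-positive rate if either day counted as success.** With no treatment effect on either day and each test at 0.05:

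rate = 1 − P(|Z₁| < 1.96 and |Z₂| < 1.96), with Z₁ and Z₂ bivariate normal.

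| Correlation | Rate |
|---|---|
| 0 (independent): 1 − 0.95² | 9.75% |
| 0.5 | 9.07% |
| 0.7 | 8.35% |
| 0.8 | 7.81% |
| 0.9 | 7.04% |

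**Step 3. How far the analysis sets can differ at Day 10.** A change-score t-test without imputation can use only people with a Day 10 score. The per-protocol set needs 10 days of evaluable data. For this test, the ITT version therefore adds only people who have a Day 10 score but lack evaluable data on some earlier day.

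**Step 4. Exposure of Day 10 to early departure.** (88 − 68) / 88 = 22.7% are expected not to complete the 10 days.

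**The case against.** The strongest reply is that the plan has already chosen. The Aim 1 text gives the outcome, the day, the test, the sidedness and the alpha, and it is the only place that ties the primary outcome to a single day. The other sections can be read as a loose list of what will be computed. Much of this stands: the intent is recoverable, and it would be too strong to say that the plan nowhere identifies a primary outcome. What does not stand is that this settles the analysis. The sentence sits in the sample-size justification, while the endpoint and methods sections call both days primary, and nothing says which text governs.

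A second reply is that this is a pilot. However, the aim is worded as a test of significance and the sample size is built on one.

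A third is that the error inflation is hypothetical. That is correct. It depends on an either-day rule that the plan does not contain, and on an assumed correlation.

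A reader might also infer more than the documents support:

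- *That the trial is underpowered because both days must be significant.* The plan has no such rule.
- *That the sample size is wrong.* It reproduces for the single Day 10 test.
- *That the unnamed analysis set leaves two quite different Day 10 tests.* Step 3 shows that they overlap heavily. It also shows that a Day 10 t-test labelled ITT is really an available-case analysis.
- *That a score taken at early discharge would be treated as Day 10.* The plan says "If a participant is discharged from the Gavin Foundation CSS before Day 10, study staff will attempt to perform Visit 5" before departure, but nothing suggests that a score from that visit would be relabelled.

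**Conclusion.** The inconsistency is real and should be corrected, but it leaves the design intact. The power section supports one Day 10 test. The endpoint and methods sections set out two unranked primary tests, and the primary analysis set is not named. This conclusion rests on the text alone and needs no assumption.

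The size does need assumptions. If either day could carry the claim, the error rate would be about 7% to 9% at correlations of 0.9 to 0.5, instead of 5%. If Day 10 alone decides, the error rate is the nominal 5% and power is 81.2% under the plan's inputs. Those inputs are stated for the IRLS scale. Whether they hold for the five-item, 24-hour subscale is a separate question, not assessed here.

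**What to change.** Amend Study endpoints and the Primary analysis paragraph to agree with the Aim 1 text:

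1. The only primary test, at two-sided 0.05, is the between-group difference in IRLS subscale change from randomization to Day 10. It is done by two-sample t-test in ITT participants who have a Day 10 score.
2. The Day 5 t-test, the per-protocol analysis and the longitudinal mixed model are supportive, reported as estimates with confidence intervals. The word "also" in the mixed-model item fits this role, but the plan should state it.
3. The mixed model uses all post-randomization IRLS scores and is named as the sensitivity analysis for missing Day 10 scores.
4. The amendment is written before its authors know any unblinded interim estimate. This matters because the interim result can end the trial: "If the needed sample size is equal to or larger than the originally projected sample size, we will close the study".

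The change adds no participants, visits or assessments, and the sample size stays as it is. It has two costs. The sponsor gives up a stand-alone primary claim on Day 5. The primary result also rests on the day most exposed to early discharge, with 22.7% of those randomized expected not to complete. The mixed model addresses that exposure but does not remove it.

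### The interim continue-or-close rule ignores the direction of the effect, and its estimate is not stated to be the Day 10 change on which the 34 per arm was set

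*Combined protocol and SAP*

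**What the plan says.** Three parts of Section IX bear on this point.

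- **Interim estimate.** The overview of the analytic plan says "We will use the data obtained to date to estimate the effect of randomized treatment group on two outcomes", IRLS and SOWS. Under Statistical Methods, Interim analysis, two-sample t-tests are applied "to estimate the effect of randomized treatment group on IRLS subscale score, for the subjects with post-randomization data to date". The same is done for SOWS. Each estimated effect then goes into a power analysis that gives the sample size needed to detect it.
- **Sizing.** Power/Sample Size, Aim 1, says "The primary outcome is the change in IRLS scale from baseline to Day 10". For 34 patients per arm it then states that "we will have 80% power to detect a 6.3 points difference in the change of IRLS scale". The SD behind this, 9.0, is that of the change, and the calculation is for a two-sided t-test at the 5% level.
- **Decision.** The Note that closes Power/Sample Size says "If the needed sample size is smaller than the originally projected sample size, we will continue the study". If the needed size equals or exceeds the projected one, the study closes. The Note reports 35 patients randomized against a projection of 68. Elsewhere in Section IX the plan is to randomize 88 so that 68 complete.

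No section makes continuation depend on the estimate favouring pramipexole, names the day or days used at the interim, or says which outcome decides if IRLS and SOWS disagree.

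**The concern.** The rule reduces the interim result to one number, needed sample size, and that number carries no sign. An effect of a given size in favour of placebo passes as easily as the same effect in favour of pramipexole. The aims are directional, so a futility rule that can pass a result in the wrong direction does not do its job in that case.

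The comparison of needed with projected size is meaningful only if both refer to the same quantity. The projected size rests on the SD of the change to Day 10. The interim text speaks of a subscale score in anyone with post-randomization data, and IRLS is scheduled on Days 1, 3, 5, 7, 9 and 10. A score and a change generally have different SDs, and an early day may show a smaller effect than Day 10. Either difference could close or continue the trial for reasons unrelated to whether the drug works. With two outcomes and one rule, a split result has no defined consequence.

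**Working it through.** **Inputs from Section IX.** Difference 6.3, SD of change 9.0, two-sided alpha 0.05, power 80%, 34 per arm, 35 randomized when the interim was added. The comparator is 34 per arm (68 in total) or 44 per arm (88 in total), because the projected size can be read either way.

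**Inputs assumed.** All 35 patients are usable, split 17 v 18 (the number with usable data is not given). Where a raw score is considered, the baseline and follow-up SDs are equal, with correlation rho from 0.2 to 0.7.

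**1. The plan's own figure.** The normal approximation is n per arm = 2(1.960 + 0.842)² × (SD/difference)² = 15.70 × (9.0/6.3)² = 32.04, so 33. The t-test calculation gives 33.02, so 34. Power with 34 per arm is 81.2%. The stated figure reproduces.

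**2. Sign.** The difference enters squared, so +7 and -7 points give the same result: 26.9, so 27 per arm or 54 in total. That is below 68, and the rule says continue even when the 7 points favour placebo.

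**3. Threshold.** The standardized difference that needs exactly 34 per arm is 0.690, or 0.690 × 9 = 6.2 points. For 44 per arm it is 0.604, or 5.4 points. Any larger difference in either direction means continue. If needed size is rounded up to whole patients first, the thresholds are 6.3 and 5.5 points.

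**4. Chance of continuing on a wrong-direction result.** With 17 v 18 patients, k = √(17 × 18/35) = 2.957. The observed t must lie below -0.690 × 2.957 = -2.039 (34 per arm) or -0.604 × 2.957 = -1.786 (44 per arm), on 33 degrees of freedom. The noncentrality is the true standardized difference times k.

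| True effect of pramipexole (SD 9) | Comparator 34 per arm | Comparator 44 per arm |
|---|---|---|
| None | 2.5% | 4.2% |
| 3 points worse | 15.7% | 22.1% |
| 6.3 points worse | 51.8% | 61.4% |

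Rounding to whole patients lowers these by about 1 percentage point or less.

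**5. Effect of a direction condition.** If only estimates favouring pramipexole can continue, the chance of continuing becomes 0.2-0.4% when the drug is truly 3 points worse and about 0.01% or less when it is 6.3 points worse. When it is truly 6.3 points better, the chance stays at 52-61%.

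**6. Score versus change.** With equal SDs, Var(change) = 2(1 - rho) × Var(score), so SD of score = 9.0/√(2(1 - rho)). For the same 6.3-point difference, the t-test calculation gives:

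| Assumed rho | SD of score | Needed per arm |
|---|---|---|
| 0.2 | 7.12 | 22 |
| 0.3 | 7.61 | 24 |
| 0.5 | 9.00 | 34 |
| 0.7 | 11.62 | 55 |

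At rho 0.2 a raw score would continue. At rho 0.7 it would close against either comparator. Change itself needs 34.

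**7. Day.** If the effect on the day used were 75% of the Day 10 effect (an assumed fraction), the needed size would be 58 per arm, which means close against either comparator.

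**The case against.** **The endpoint may be shorthand.** Study endpoints in Section IX uses IRLS score as the name of the primary outcome and then says the primary analyses concern change. The interim overview uses the same name. A reader might infer that the interim definitely uses a different endpoint, but the documents do not support that. They support only that the interim is not stated to use change to Day 10. The score-versus-change figures apply only if a raw score was meant. The day stays open even if change was meant, because the primary analysis itself uses both Day 5 and Day 10.

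**The interim population is not odd.** The plan's intent-to-treat set also requires only one dose and one assessment after randomization. A reader might also infer that patients with data only to Day 3 have not reached the dose review. Visit 4 is scheduled for Day 3 (Day 4 or 5 if delayed), so what they lack is data after any dose change.

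**Harm is unlikely and would be seen.** A reader might infer from the 52-61% that the trial is likely to continue with a harmful drug. Those figures assume a truly adverse effect on RLS, whereas the background describes dopamine agonists as efficacious for primary RLS. The t-test estimate is signed, an unblinded statistician sees it, and a DSMB reviews progress and adverse events. This lowers the practical risk but does not replace a criterion. The Note contains no direction condition, Section X gives the DSMB no part in this decision, and IRLS is not in its list of data monitored for safety.

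**The rule is about feasibility.** The Note frames futility as whether the needed number can be recruited with available resources. That explains the form of the rule. It does not explain why a result favouring placebo should pass.

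**Conclusion.** The point stands as a gap in a stated decision rule. As written, an observed difference of about 6.2 points or more in favour of placebo at SD 9.0 means continue (5.4 points against 44 per arm). With no true effect the chance of this is 2.5-4.2%. The larger figures, 16-22% and 52-61%, are conditional on pramipexole being truly 3 or 6.3 points worse and should not be read as likely. All of these rest on an assumed 17 v 18 usable patients.

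The endpoint part is an ambiguity, not a demonstrated mismatch. If a raw score were used, needed size for the same 6.3 points would run from 22 to 55 per arm at an assumed rho of 0.2 to 0.7, against 34 for change, which is enough to move the decision either way. The lack of a deciding outcome is plain on the text: two needed sample sizes are computed and the rule refers to one.

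**What to change.** Add to the interim section and the Note:

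1. The study continues only if the interim estimate favours pramipexole and the needed sample size is below the projected one.
2. The interim estimate is the unadjusted difference in IRLS subscale change from randomization to Day 10, in patients with a Day 10 value. Unadjusted matters, because the 34 per arm rests on the unadjusted SD of change. Under the equal-SD assumption, baseline adjustment would multiply needed size by (1 + rho)/2, for example 0.75 at rho 0.5, and the comparison would again not be like for like.
3. IRLS alone decides, and the SOWS result is descriptive.

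The text costs a few sentences. The analytic cost is that patients without a Day 10 value do not contribute to the decision. At the planned completion rate, 35 × 68/88 = 27 patients would remain. With 14 v 13, the chance of continuing when the drug is truly 6.3 points better is little changed (52-60%). With no true effect, the chance of continuing on a favourable estimate rises from 2.5-4.2% to 4.3-6.5%.
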